3.4 Secondary Endpoints

Secondary endpoints will be examined to provide additional support and details of the primary endpoint findings concerning the RFA treatment. The secondary endpoints assess important patient-based clinical outcomes to compliment the biophysiological primary outcomes. It will be evaluated using mean change at 6-months follow-up from baseline. As supporting evidence, this will be tested with one-sided confidence interval with no corrections for multiple testing.

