3.4.1.2 Objective and Hypotheses

The FOSQ secondary endpoint in this study will be determined by the FOSQ score at the 6-month follow-up compared with the pre-treatment Baseline. The objective is to demonstrate an improvement of daytime sleepiness measured by the FOSQ.

$$H_0: \mu_{FOSQ} \leq 0$$

$$H_A: \mu_{FOSQ} > 0,$$

where μ_{FOSQ} is the mean change of FOSQ from pre-treatment baseline to the 6-month post-treatment follow-up. This hypothesis will be tested using one-sided 95% confidence interval around the mean FOSQ.

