3.4.2.2 Objective and Hypotheses

The ESS secondary endpoint in this study will be determined by the ESS score at the 6-month follow-up compared with the pre-treatment Baseline. The objective is to demonstrate an improvement of daytime sleepiness measured by the ESS.

$$H_0: \mu_{ESS} \leq 0$$

$$H_A: \mu_{ESS} > 0,$$

where μ_{ESS} is the mean change of ESS from pre-treatment Baseline to the 6-month post-treatment follow-up. This hypothesis will be tested using one-sided 95% confidence interval around the mean ESS.

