3.4.3.2 Objective and Hypotheses

Seite 23 von 54

Protocol 990211 RAMOSA

RFA for multi-level OSA

Protocol version 6.0 from 26th September 2014

The VAS_{snoring} secondary endpoint in this study will be determined by the VAS score at the 6-month follow-up compared with the pre-treatment Baseline. The objective is to demonstrate a reduction in snoring.

$$H_0: \mu_{VAS} \geq 0$$

$$H_A: \mu_{VAS} < 0,$$

where μ_{VAS} is the mean change of VAS from pre-treatment Baseline to the 6-month post-treatment follow-up. This hypothesis will be tested using one-sided 95% confidence interval around the mean VAS_{snoring}.

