7 INSTRUMENTS

The following outcome measures will be utilized to represent meaningful measurements of therapy success:

1. Apnea-hypopnea index (AHI) - is an index of sleep apnea severity that combines the frequency of apnea and hypopnea events. The severity of obstructive sleep apnea is determined by the measurement of apneas and hypopneas. An obstructive apnea is defined as a cessation (> 90% decrease) of airflow for at least 10 seconds with breathing effort; and a hypopnea is defined as an event with at least a 30% reduction in airflow lasting at least 10 seconds, and with $\geq 4\%$ oxygen desaturation. The frequency of apneas and hypopneas per hour of sleep is termed the apnea-hypopnea index (AHI). AHI values are typically categorized as 5–15/hr = mild; 15–30/hr = moderate; and $> 30/h$ = severe. AHI will be determined at baseline and at the 6-months follow-up visit.
2. Oxygen Desaturation Index (ODI) – ODI is defined as the number oxygen desaturation events, where there is a $\geq 4\%$ desaturation from pre-event baseline, that occur per hour of sleep. ODI generally correlates well with AHI [15], and it is reasonable to conclude that a 25% reduction in ODI represents a

Seite 34 von 54

Protocol 990211 RAMOSA

RFA for multi-level OSA

Protocol version 6.0 from 26th September 2014

clinically meaningful improvement. ODI will be determined at baseline and at the 6 months follow-up visit.

3. Epworth Sleepiness Scale (ESS) - The ESS is a validated, self-report instrument that rates a subject's tendency to fall asleep in eight common daily situations. The ESS Scale has been validated primarily in OSA. It is used to measure excessive daytime sleepiness, and is often utilized before and after the administration of treatment (e.g. CPAP) to document improvement of symptoms. The patient will complete this questionnaire at the Baseline, at Visit 3 (prior to the 1st RFA treatment), Visit 4 (prior to the 2nd RFA treatment), at Visit 5 (prior to the 3rd RFA treatment), at Visit 6 (6 weeks follow-up post 3rd RFA treatment), and at Visit 7 (6 months follow-up).

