8.1 Primary Efficacy Endpoint

The primary endpoint of AHI and ODI obtained at the 6-month follow-up will be compared to the Baseline measurement. The subject is a responder if the reduction in AHI is $\geq 50\%$, and ODI reduction is $\geq 25\%$. The proportion of subjects meeting the responder criteria among all included subjects will be evaluated using a one-sided 95% confidence interval. In addition one sample test of the proportion of patients meeting the PG at 6month is significantly different than 50%. The study is designed to demonstrate success rate of 20% beyond the PG of 50%. Proportion with 95% CI will be given using normal approximation to the Binomial. P-Value will be derived based on the exact binomial distribution of the null hypothesis, that is assuming $p=0.5$.

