8.2 Additional Analysis

Demographic, medical history and operative characteristics will be summarized for the study cohort, by clinical site, and by groupings of all sites. At a minimum, this will include age, gender, race, weight, and BMI.

Supporting analyses will be conducted to provide additional information on the safety and efficacy of multi-level radiofrequency treatment. Descriptive statistics will be utilized to summarize all adverse events. Regression models evaluating the change of continuous outcomes of AHI and ODI as well as logistic regression for the categorical outcome of response to treatment as defined in the primary objective will be used. A description of the relationship between BMI change and effectiveness outcomes will be performed by a cross-tabulation of BMI change versus responder and non-responder groups.

Data collected on all enrolled study subjects will be analyzed on an intend-to-treat and as-treated basis. Disease information and demographic variables, such as age, ethnic group, and sex, will be summarized by means of summary statistics. A normality distribution test (Kolmogorov-Smirnov) will be performed for all variables. Simple descriptive statistics such as frequency, mean, standard deviation, minimum, and maximum will be calculated for all outcome variables. If these variables are not normally distributed, other descriptive measurements such as median and the interquartile range will be calculated. For comparison between pre- and post-treatment variables, McNemar's-will be used with categorical variables. For continuous variables, a paired t-Test (normal distribution) or a Wilcoxon signed rank Test (not normal distribution) will be used to compare data at visit 2 (Baseline) and at visit 6 (six weeks after final RFA treatment). In addition, for long longitudinal analysis a One-Way ANOVA with Repeated Measures (or mixed models) will be used to model the outcome and cofactors over the multiple time-points. Significant interactions will be followed up using post-hoc analysis with Holms' adjusted P-values.

Site homogeneity will be evaluating by testing the interaction term in the analysis of covariance (ANCOVA) at a significance level of 0.15.

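### Section 8.2 ties the paired pre/post test to Visit 6, but every efficacy endpoint is set at 6 months (Visit 7) and no PSG is scheduled at Visit 6; the error is confined to supporting analyses

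*Combined protocol and SAP*

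**What the plan says.** Section 8.2 (Additional Analysis) gives one rule for continuous pre/post variables: a paired t-test, or a Wilcoxon signed rank test if normality fails. The chosen test "will be used to compare data at visit 2 (Baseline) and at visit 6 (six weeks after final RFA treatment"). The rule exempts no continuous variable. The next sentence adds a repeated-measures ANOVA or mixed model, which "will be used to model the outcome and cofactors over the multiple time-points"; it lists no visits and names no contrast.

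The endpoints are set at another visit:

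- Primary (8.1): "The primary endpoint of AHI and ODI obtained at the 6-month follow-up will be compared to the Baseline measurement".
- Secondary endpoints in general (3.4): "It will be evaluated using mean change at 6-months follow-up from baseline".
- FOSQ (3.4.1.2): "will be determined by the FOSQ score at the 6-month follow-up compared with the pre-treatment Baseline".
- ESS (3.4.2.2): "will be determined by the ESS score at the 6-month follow-up compared with the pre-treatment Baseline".
- Snoring VAS (3.4.3.2): the "secondary endpoint in this study will be determined by the VAS score at the 6-month follow-up compared with the pre-treatment Baseline".
- Percentage sleep time at SaO2 < 90% (3.4.4.2): the 6-month PSG against the baseline PSG.

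On measurement times, Section 7 states that "AHI will be determined at baseline and at the 6-months follow-up visit", and gives the same two times for ODI. Section 5.6 lists history, examination, ESS, FOSQ and VAS scales for Visit 6, with no PSG. Section 5.7 attaches the second PSG to Visit 7, and Appendix I marks PSG and ODI at Visits 2 and 7 only.

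**The concern.** Section 8.2 is the only place that names a paired test, and the only place that says what to do if a continuous outcome is not normally distributed. Both instructions point to a visit at which no efficacy endpoint is defined and no PSG variable is measured. An analyst following the sentence literally would have no data for the PSG outcomes. For the questionnaires and snoring VAS, the analyst would produce a p-value for an early response.

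The protocol has its own reasons for preferring the later visit. Section 2.5 picks 6 months partly because that is long enough to see whether the effect strengthens or fades. Section 1.3 describes a second phase of tissue shrinkage that takes several months. A six-week contrast answers a different question.

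Two things are at stake. One is whether a 6-month analysis is pre-specified for skewed secondary outcomes. The other is how readers will weigh a named Visit 6 test against the 6-month interval, in an open-label single-arm study whose symptom outcomes are subjective.

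**Working it through.** **1. Which outcomes have data for Visit 2 versus Visit 6?**

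| Outcome | Endpoint time | Measured at Visit 6? | Test in 8.2 as written |
|---|---|---|---|
| AHI | 6 months (3.1, 8.1) | No PSG (5.6, 7, Appendix I) | Cannot be run |
| ODI | 6 months (3.1, 8.1) | No PSG | Cannot be run |
| % sleep time at SaO2 < 90% | 6-month PSG (3.4.4.2) | No PSG | Cannot be run |
| ESS | 6 months (3.4.2.2) | Yes | Runs, before the endpoint visit |
| FOSQ | 6 months (3.4.1.2) | Yes | Runs, before the endpoint visit |
| Snoring VAS | 6 months (3.4.3.2) | Yes | Runs, before the endpoint visit |

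Three of the six outcomes have no Visit 6 value. The other three have one at a visit that is not the endpoint.

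One statement could suggest otherwise. Section 1.2 says the WatchPAT home study is repeated at both follow-up visits, which would give a device-based AHI at Visit 6. That is not PSG, and it is to be compared with screening rather than with Visit 2. It is also absent from Section 5.6, and Appendix I marks WatchPAT at Visit 1 only. It does not rescue the test.

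**2. How early is Visit 6?** Inputs: third RFA by week 18 and Visit 6 by week 24 (Appendix I, both upper limits). Assumption: 6 months is about 26 weeks.

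- Visit 7 counted from the last RFA (Section 5.7 heading): 18 + 26 = week 44; 44 − 24 = 20 weeks.
- Visit 7 counted from Visit 6 (a possible reading of Section 6, with its total of 24 weeks plus 6 months, and of the time row in Appendix I): 24 + 26 = week 50; 50 − 24 = 26 weeks.

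**3. Do the sample size and power depend on it?** Section 3.2 gives n = 43, P0 = 0.50, P1 = 0.70 and rejection at Z ≥ 1.96.

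- Rejection threshold: 43 × 0.5 + 1.96 × √(43 × 0.25) = 21.5 + 6.43 = 27.93, so reject at 28 or more responders.
- Exact binomial: P(X ≥ 28 | 0.50) = 0.0330 and P(X ≥ 28 | 0.70) = 0.8081.

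These match the 0.0330 and 0.8081 in Section 3.2 and the 80.8% in Section 8.3. The calculation concerns the 6-month responder proportion and contains nothing that depends on Visit 6.

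**4. What does the plan already specify at 6 months?** Section 8.1 sets the primary test there. Sections 3.4.1 to 3.4.4 each test mean change to 6 months with a one-sided 95% confidence interval. If that interval is t-based, which the protocol does not say, it is equivalent to a one-sided paired t-test at 5%. No section gives a 6-month alternative for non-normal data.

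**The case against.** The strongest reply is that nothing here contradicts the endpoints. Section 8.2 describes supporting analyses. Section 3.3 plans ESS, FOSQ and snoring VAS six weeks after the treatments as well as at 6 months, so a six-week contrast is legitimate. The sentence does not claim to replace the endpoint tests, and the longitudinal model that follows may be meant to cover the later visits.

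Much of this stands, and it rules out four stronger readings that a reader might infer:

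- That symptom change would be tested only at six weeks. Sections 3.4.1 to 3.4.3 test it at 6 months.
- That the PSG outcomes have no analysis. Section 8.1 covers AHI and ODI at 6 months, Section 3.4.4.2 covers oxygen saturation time, and Section 8.2 separately plans regressions for change in AHI and ODI.
- That the endpoint visit is left open to choice after the data are seen. Section 3.4 and its subsections fix it at 6 months. What remains is a risk of over-emphasising a Visit 6 p-value.
- That the gap is exactly 20 weeks. The documents allow about 20 to 26.

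The reply does not cover everything. The rule is written for continuous variables without exception, yet half of the efficacy variables cannot enter it. The longitudinal model names neither Visit 7 nor a 6-month contrast. And the non-normal fallback exists only in the sentence tied to Visit 6. Nor can the sentence be read as a slip in the visit number, because its parenthesis describes Visit 6 correctly.

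**Conclusion.** The paired-test rule in Section 8.2 is wrong as written, within supporting analyses. It cannot be carried out for AHI, ODI or percentage sleep time at SaO2 < 90%. For ESS, FOSQ and snoring VAS it falls about 20 weeks before the endpoint visit, or about 26 weeks if Visit 7 is counted from Visit 6. Both figures take 6 months as about 26 weeks and use the latest scheduled weeks.

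The primary conclusion, the 6-month secondary intervals, the sample size and the power stand. The substantive loss is that a Wilcoxon test is not specified at 6 months if a secondary outcome is clearly non-normal. The correction is worth making before analysis, but it does not put the trial's main result in doubt.

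**What to change.** Revise Section 8.2 as follows:

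1. Make baseline versus Visit 7 (6-month follow-up) the comparison for the paired t-test or Wilcoxon test. State that this is also the fallback for the secondary endpoints in Section 3.4 when normality fails.
2. Keep any Visit 6 comparison of ESS, FOSQ and the VAS scales, labelled as intermediate and supporting.
3. List the visits in the repeated-measures or mixed model and name the 6-month contrast.
4. Say which visit supplies the baseline for each VAS. Section 5.2 lists only ESS and FOSQ as Visit 2 questionnaires, Section 5.3 collects snoring, speech and swallowing VAS before treatment at Visit 3, and Appendix I also marks snoring VAS at Visit 2.

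Two related statements should be reconciled in the same edit: the origin of the 6-month count (Section 5.7 against Section 6 and Appendix I), and the repeat WatchPAT in Section 1.2 against the visit schedule.

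The cost is a few sentences. The paired-test changes need no extra patients, visits or measurements.

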2.2 Scale

The study will be conducted at a maximum of 3 centers in which at least one study center will be in the United States. Patients will be enrolled to provide data from up to 48 subjects. Data from 43 subjects is required to demonstrate efficacy and we count 10% for dropouts (Section 3.2 Sample Size Rational). When the treatment limit of 48 subjects is reached, Sponsor may opt to submit for expanded access.

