3.1.1 Experimental Design

This is a single-arm assessment of AHI responder rate for treatment of obstructive sleep apnea compared to a performance goal (PG). Patients with 6-month post-treatment AHI measurements will be counted as a responder if they meet the performance goal. A subject will be counted as a non-responder (regardless of AHI measurement at 6 months) under the following circumstances:

- a. Death (any cause) between treatment and the 6-month follow-up
- b. Unsuccessful radiofrequency treatment attempt
- c. Need for an alternative OSA treatment before the 6-month follow-up
- d. Subjects who abandon the study
- e. Subjects who exit the study after the last treatment, but before the 6-month follow-up

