4 RESEARCH DESIGN

The study is a prospective, single-arm, multicenter study designed to determine the effectiveness of multi-level radiofrequency ablation (RFA) for mild to moderate obstructive sleep apnea. The study aims to recruit a total of 48 patients at 3 study sites. The Medical University of South Carolina Hospital will serve as the primary site with [REDACTED] the PI of the study.

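### The site-homogeneity check in section 8.2 tests an undefined ANCOVA interaction, so this single-arm trial has no specified test of whether responder rate differs between sites

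*Combined protocol and SAP*

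**What the plan says.** Section 4 describes the design: "The study is a prospective, single-arm, multicenter study designed to determine the effectiveness" of multi-level ablation. Section 2.2 sets the number of sites: "The study will be conducted at a maximum of 3 centers". Section 8.1 defines the primary result as one proportion over everyone included: "The proportion of subjects meeting the responder criteria among all included subjects will be evaluated using a one-sided 95% confidence interval". Section 3.1.3 sets the performance goal at 50%.

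The only analysis of site differences is in section 8.2: "Site homogeneity will be evaluating by testing the interaction term in the analysis of covariance (ANCOVA) at a significance level of 0.15". The sentence does not say which outcome is modelled, which terms interact, or what follows from a significant result.

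Three other parts of section 8.2 come close without filling the gap:
- By-site summaries are planned for demographic, medical history and operative characteristics. Response is not listed.
- For the binary endpoint, "logistic regression for the categorical outcome of response to treatment as defined in the primary objective will be used", but no covariates are named and site is not mentioned.
- A repeated-measures ANOVA or mixed model is planned over the visits, with follow-up of significant interactions. No site term is named.

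**The concern.** In a randomised multicentre trial, an interaction test for site homogeneity normally means treatment by site: does the difference between arms vary across centres? This trial has no second arm, so that term cannot be formed. In a single-arm trial the corresponding question is answered by the site main effect: does the outcome itself differ between sites?

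ANCOVA is also a model for a continuous outcome, whereas the primary endpoint is responder or non-responder. Whatever interaction was meant, the sentence does not lead to a comparison of responder rates between sites.

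The stake is interpretive. The answer will be one pooled rate from up to three centres, for an operator-dependent procedure; section 1.5 lists the surgeons' learning curve among factors that may affect complications. A reader will want to know whether the pooled rate describes all the sites or averages over quite different ones. The planned check is poorly suited to showing that.

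**Working it through.** **1. The plan's own figure.** The site sentence carries no derived figure, only the level 0.15. The nearest is the power in sections 3.2 and 8.3. With n = 43, P0 = 0.50 and P1 = 0.70, the rule is to reject if (r/43 − 0.5)/√(0.25/43) ≥ 1.96.
- r = 27 gives 0.1279/0.0762 = 1.68, so no rejection.
- r = 28 gives 0.1512/0.0762 = 1.98, so rejection.
- The exact binomial rule r ≥ 28 has alpha 0.0330 and power 0.8081, as stated.
- 43/(1 − 0.10) = 47.8, which rounds up to the stated 48.

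These figures are sound and do not depend on the site check.

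**2. What the interaction could be.**
- *Treatment by site:* not available, because there is one arm.
- *Site by baseline covariate:* compares the slope of outcome on baseline between sites.
- *Site by time in the longitudinal model:* compares mean change between sites for a continuous outcome.

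None of these tests responder rate by site.

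**3. How the site-by-baseline reading behaves.** Assumptions, none from the documents except the AHI range 10–30: three sites of 16, baseline AHI uniform on 10–30, normal residuals. The model is AHI change on baseline and site, with and without site × baseline. The interaction F test has 2 and 48 − 6 = 42 df; the site main-effect F test has 2 and 48 − 4 = 44 df. Both are at 0.15.

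| Assumed site differences | Residual SD | Interaction rejects | Site main effect rejects |
|---|---|---|---|
| None | 7 | 16% | 15% |
| Mean shift −3/0/+3 events/h, equal slopes | 7 | 16% | 75% |
| Mean shift −5/0/+5 events/h, equal slopes | 7 | 15% | 99% |
| AHI reduced by 30/50/70% | 7 | about 26% | about 91% |
| AHI reduced by 30/50/70% | 4 | about 45% | over 99% |

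In the last two rows the slopes of change on baseline are −0.3, −0.5 and −0.7, so the slope test has something to find. At the mean baseline of 20, the mean changes are 0.3 × 20 = 6, 0.5 × 20 = 10 and 0.7 × 20 = 14 events/h. The main-effect test picks up this spread far more readily.

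**4. What a direct test of responder rate can do.** Full enumeration of three binomials with 16 per site (48/3), 2 df, level 0.15. Site rates are assumptions.

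| True rates by site | Asymptotic chi-square | Exact test |
|---|---|---|
| 40/70/70% | 0.615 | 0.58 |
| 40/60/80% | 0.741 | 0.71 |
| 80/70/60% | 0.37 | 0.29 |

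Under equal 60% rates the asymptotic test rejects with probability 0.143. With the 43 evaluable patients split 15/14/14, the 80/70/60% row becomes 0.34 (asymptotic) and 0.33 (exact). A 20-point spread around the design rate of 70% would therefore be missed in roughly two trials out of three, or more.

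**The case against.** The best defence is that the sentence can be given a workable meaning. It follows directly on the repeated-measures or mixed model and the handling of its interactions, so site by time is a natural reading. In a single-arm pre/post model, that term asks whether mean change differs between sites, which for AHI and ODI is close to the right question. This stands as a possible reading, so it would be wrong to infer that site by baseline is the only alternative or that the check cannot be run. But the sentence says ANCOVA, does not name site by time, and would still leave responder rate untested.

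A reader might also infer that the slope test would declare sites homogeneous however much they differ. That goes too far: the 15% rejection rate holds only if sites differ in level and share a slope. Because the endpoint is built on a percentage reduction, site differences may show partly in the slopes, as the 26% to 45% figures illustrate. The test is weak, not blind.

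A third tempting inference is that pooling, and hence the trial's conclusion, rests on this check. The documents do not say so. Section 8.1 defines the proportion over all included subjects without condition, section 8.2 gives no pooling rule, and the sentence stands under additional analyses.

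Finally, the planned logistic regression could include site. It could, but the plan does not say that it will.

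**Conclusion.** The point holds as a defect in a supporting analysis. The term to be tested is undefined, its usual meaning does not exist in a single-arm trial, and no reading of it tests responder rate between sites. On the slope reading, the check rejects at 15% to 45% in the scenarios with site differences, where a site main-effect test rejects at 75% to over 99%. Those figures rest on assumed equal sites of 16, uniform baseline AHI, residual SD 4 or 7, and assumed site effects.

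Nothing here changes the primary test's alpha, power or pooling. What is lost is a valid check of consistency across up to three sites. The correct test will itself have limited power with about 14 to 16 patients per site, so a non-significant result should not be read as proof that the sites agree.

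**What to change.** Replace the sentence in section 8.2 with three elements:

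1. Test the site main effect on response at 0.15, either by an exact test on the site-by-response table or with site as a factor in the logistic regression already planned.
2. Report the responder rate with a confidence interval for each site. With so few patients per site, these estimates will tell the reader more than the p-value.
3. For AHI and ODI, fit an ANCOVA of the 6-month value on site with the baseline value as covariate, and test the site term.

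Add that the homogeneity test has limited power at this sample size, and say how a significant result will be reported. The cost is a few lines of text, with no new data, visits or patients. The downside to accept openly is that the test will often miss moderate differences.
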